5.1. Determination of Sample Size

Approximately 500 patients will be randomized at a 4:1 ratio in the blinded Induction Period to receive 250 mg mirikizumab or placebo SC at Weeks 0, 4, 8, and 12. Stratified block randomization will be performed with the following stratification factors: previous exposure to biologic therapy (yes/no), body weight (<100 kg or ≥100 kg), and geographic region (North America or Other).

There are multiple primary endpoints in this study: static Physician’s Global Assessment (sPGA) (0,1) and PASI 90 at Week 16. The assumed sPGA (0,1) responses are 70% for the mirikizumab arm and 5% for the placebo arm. The assumed PASI 90 responses are 70% for the mirikizumab arm and 3% for the placebo arm. These assumptions are based upon the results of

the mirikizumab Phase 2 Study AMAF (Reich et al. 2017) and review of historical clinical studies in psoriasis (Langley et al. 2014; Gordon et al. 2016; Blauvelt et al. 2017; Papp et al. 2017; Reich et al. 2017).

With a total sample size of 500 patients, randomizing 400 patients to the mirikizumab arm and 100 patients to the placebo arm, this study has power of >95% for testing superiority of mirikizumab to placebo based on a 2-sided chi-square test with alpha of 5% on sPGA(0,1). It also provides a power of >95% for testing superiority of mirikizumab to placebo on PASI 90 based on a 2-sided chi-square test with alpha of 5%.

In order to account for multiple testing for the comparisons of 2 mirikizumab groups against the placebo group in the Maintenance Period, a 2-sided chi-square test at the 0.025 level is assumed. Assuming 70% of the mirikizumab patients are re-randomized in the Maintenance Period at Week 16 (Visit 7) at a 1:1:1 ratio to 250 mg mirikizumab Q8W, 125 mg mirikizumab Q8W or placebo, approximately 93 patients will be included in each treatment group. Stratified block randomization will be performed with the stratification factor of body weight at baseline (<100 kg or \geq 100 kg). This sample size will provide >95% power to test the difference in the proportion of patients maintaining PASI 90 from Week 16 (Visit 7) after re-randomization at the start of the Maintenance Dosing Period to Week 52 (Visit 16) between each mirikizumab dosing interval and placebo, assuming the proportions of patients maintaining PASI 90 are 80% for 250 mg mirikizumab Q8W, 70% for 125 mg mirikizumab Q8W, and 10% for placebo.

5.2. Method of Assignment to Treatment

Patients who meet all criteria for enrollment will be randomized to double-blind treatment at Week 0 and to re-randomize patients at Week 16. Stratified block randomization will be implemented using a computer-generated sequence within an interactive web-response system (IWRS). Randomization will be stratified, based on previous exposure to biologic therapy (yes/no), body weight (<100 kg or \geq 100 kg), and geographic region (North America or Other). The IWRS will be used to assign prefilled syringes containing double-blind investigational product to each patient. Site personnel will confirm that they have located the correct carton(s) of pre-filled syringes by entering a confirmation number found on the carton(s) into the IWRS.

6. A Priori Statistical Methods

6.1. General Considerations

Statistical analysis of this study will be the responsibility of Eli Lilly and Company (hereafter, Lilly) or its designee. The latest version of the Medical Dictionary for Regulatory Activities (MedDRA[®]) will be used.

Analyses and summaries from assessment of endpoints described in the protocol (e.g., described in [Table AMAK.4.1](#) and in Section 4 of AMAK protocol) are planned to be included in the clinical study report (CSR). Analyses and summaries for key safety data are also planned to be included in the CSR. Results from additional efficacy analysis pre-defined below and other safety analyses may also be provided in the CSR, as deemed appropriate. Any analysis or summary not included in the CSR will be available upon request.

Any change to the data analysis methods described in the protocol will require a protocol amendment ONLY if it changes a principal feature of the protocol. Any other change to the data analysis methods described in the protocol and the justification for making the change will be described in the CSR.

Additional exploratory analyses of the data may be conducted, as deemed appropriate. Some of these additional supplementary analyses will be prespecified in a separate supplemental SAP.

Some of the analyses described in this document will be incorporated into interactive display tools instead of or in addition to static displays.

The Schedule of Activities outlined in the protocol specifies the allowable windows for assessments. Assessments performed outside these windows will not be excluded from any analysis.

6.1.1. *Patient Populations for Analysis*

Patient populations are defined in [Table AMAK.6.1](#) along with the analysis they will be used to conduct. Patients will be analyzed according to the treatment to which they were assigned for all populations. [Table AMAK.6.2](#) describes the treatment groups and the comparisons for each study period and the analysis population.

Table AMAK.6.1. Patient Populations for Analysis

Population	Description
All Entered Patients	All patients who signed informed consent.
Induction ITT	All randomized patients, even if the patient does not take the assigned treatment, does not receive the correct treatment, or otherwise does not follow the protocol. Unless otherwise noted, efficacy and health outcomes analyses for the induction period will be conducted on this population.
Induction Safety	All randomized patients who received at least 1 dose of study treatment . Safety analyses for the induction period will be conducted on this population.
Re-randomized Maintenance ITT	All Induction ITT patients who received at least 1 induction dose of study treatment and have been re-randomized at Week 16. Efficacy and health outcomes analyses for the maintenance period will be conducted on this population.
Re-randomized Maintenance Safety	All Induction ITT patients who received at least 1 induction dose of study treatment, have been re-randomized at Week 16 and have received at least 1 maintenance dose . Safety analyses for the maintenance period will be conducted on this population.
Non-re-randomized Maintenance ITT	All Induction ITT patients who received at least 1 induction dose of study treatment, have not been re-randomized at Week 16, and have entered the maintenance period (Table AMAK.6.3). Efficacy analyses for the maintenance period will be conducted on this population.
Maintenance ITT	Pooled re-randomized and Non-re-randomized populations.
Re-randomized Relapsed	All Re-randomized Maintenance ITT patients who relapse during the Maintenance Period and received a 250-mg dose. These patients will be analyzed for recapture of efficacy response.
All Miri Safety	All randomized patients who received at least 1 dose of mirikizumab . Patients who received placebo for the entire study are not included.
Induction PPS	All randomized patients who do not have important protocol deviations excluded from per protocol analysis (IPDPP) in the induction period. IPDPP are described in a separate document: “The AMAK Trial Issues Management Plan.” These patients will be used as a sensitivity analysis for the primary endpoints only.

Abbreviations: ETV = early termination visit; ITT = intent-to-treat; PPS = per protocol set.

Table AMAK.6.2. Treatment Groups and Comparisons for Each Study Period and Analysis Population

Study Period	Analysis Population	Treatment Groups	Inferential Comparisons
Induction	Induction ITT Induction Safety Induction PPS	placebo Q4W; 250 miri Q4W	250 miri Q4W vs. placebo Q4W
Maintenance	Re-randomized Maintenance ITT; Re-randomized Maintenance Safety	placebo Q8W ^e ; 125 miri Q8W; 250 miri Q8W; Total miri*	125 miri Q8W vs. placebo Q8W; 250 miri Q8W vs. placebo Q8W
	Re-randomized Relapsed	placebo Q8W ^a e; 125 miri Q8W ^a ; 250 miri Q8W ^a ; Total miri*	No comparison
	Non-re-randomized Maintenance	miri nonresponder ^b ; placebo nonresponder ^c placebo responder ^d	No comparison
	Maintenance ITT	placebo Q8W ^e ; 125 miri Q8W; 250 miri Q8W; miri nonresponder ^b ; placebo responder ^d placebo nonresponder ^c ;	No comparison
All	All Miri Safety	all miri ^f ; all miri + placebo withdrawal ^e ^f ; all miri + placebo withdrawal ^e + FUP ^f	No comparison

Abbreviations: FUP = follow-up; ITT = intent-to-treat; miri = mirikizumab; PASI 90 = $\geq 90\%$ improvement from baseline in the Psoriasis Area and Severity Index; PPS = per protocol set; Q4W = administration once every 4 weeks; Q8W = administration once every 8 weeks; vs. = versus.

* For safety related analysis only.

^a Treatment is the treatment patient was receiving immediately before relapse.

^b Patients randomized to mirikizumab in induction who do not achieve PASI 90 at Week 16 receive 250 mg Q8W.

^c Patients randomized to placebo in induction who do not achieve PASI 90 at Week 16 receive 250 mg Q8W.

^d Patients randomized to placebo in induction who achieve PASI 90 at Week 16 continue to receive placebo.

^e Patients re-randomized to Placebo in Maintenance Period.

^f Technically, there is only 1 treatment group. However, all summaries utilizing the “All Miri Safety” will include a summary for different periods:

- all miri: only the period of exposure to miri treatment.
- all miri + placebo withdrawal: period of exposure to miri treatment + placebo withdrawal.
- all miri + placebo withdrawal + FUP: period of exposure to miri treatment + placebo withdrawal + follow up.

6.1.2. Study Time Intervals

Table AMAK.6.3 displays a list of study periods along with the definition of which patients will be considered to have entered the study period and when the individuals start and end the study period. The table shows both a date and a time.

To calculate the length of any time interval or time period in this study, the following formula will be used:

$$\text{Length of interval (days)} = \text{End Date} - \text{Interval Start Date} + 1$$

To convert any time length from days to years, the following formula will be used:

$$\text{Length of interval (years)} = \text{Length of interval (days)} / 365.25$$

To convert any time length from days to weeks, the following formula will be used:

$$\text{Length of interval (weeks)} = \text{Length of interval (days)} / 7$$

Only for the purpose of calculating the length of study period time intervals, the words “prior to” in [Table AMAK.6.3](#) should be understood to mean “the day before,” while the word “after” should be understood to mean “the day after.”

Table AMAK.6.3. Definition of Study Period Time Intervals

Study Period	Start Definition	End Definition
Screening: All patients who sign informed consent are considered as entering the Screening Period.	Informed consent date	Prior to the start of induction.
Induction Period Interval: All patients who are randomized to the study are considered as entering the Induction Period.	At the first injection date/time ^a following randomization. For patients who are randomized but not dosed, the Induction Period starts on the date of randomization.	Prior to the start of maintenance. For patients who discontinue before or on the Week 16 visit, the induction period ends at the last date of treatment discontinued date or last treatment visit date.
Maintenance Period Interval: All patients who had any Week 16 to Week 52 visits (except the ones who discontinued the study at Week 16) are considered to have entered the Maintenance Period.	At the Week 16 dosing date/time ^a . If a patient is unable to be dosed at the Week 16 visit, the Maintenance Period starts at the Week 16 visit. If the patient misses the Week 16 visit, the Maintenance Period starts at Day 118.	After the Week 52 visit date. If patients discontinued prior to Week 52, the Maintenance Period ends at the last date of treatment disposition date or last treatment visit date. If the patient relapsed, the Maintenance Period ends before the patient entered the relapse period.
Relapse Period Interval: All patients who responded during induction and meet the relapse criteria and receive a 250 mg dose during maintenance will be considered to have entered the Relapse Period.	The date/time ^a the patient received the first dose ^a after the patient was measured to meet the relapse criteria.	After the Week 52 visit date. If patients discontinued prior to Week 52, the Relapse Period ends after the early treatment discontinuation visit date.
Placebo Withdrawal Interval: All patients who are re-randomized to placebo will be considered to have entered the placebo withdrawal period.	Same as start of the maintenance period.	Same as end of the maintenance period.
Follow-up Period Interval: All patients who had Visit 801 or 802 are considered to have entered the Follow-up Period.	The latest of the following dates: (1) after the end of the Induction Period; (2) after the end of the Maintenance Period; (3) after the end of end of the Relapse Period.	The last date of the last study visit and study disposition date.

Study Period	Start Definition	End Definition
All Miri^b: All patients who are treated with mirikizumab are considered to have entered this period.	The date/time ^a of first injection with mirikizumab (i.e., injection with placebo does not start the period).	If the patient is not re-randomized to Placebo, then the All Miri Period ends the latest of the following dates: (1) after the end of the Induction Period; (2) after the end of the Maintenance Period; (3) after the end of end of the Relapse Period. If the patient is re-randomized to Placebo, then the All Miri Period is the combination ^b of the Induction and Relapse Periods (if the patient relapses).
All Miri + Placebo Withdrawal Period: All patients who are treated with mirikizumab are considered to have entered this period.	The date/time ^a of first injection with mirikizumab (i.e., injection with placebo does not start the period).	The latest of the following dates: (1) after the end of the Induction Period; (2) after the end of the Maintenance Period; (3) after the end of end of the Relapse Period.
All Miri + Placebo Withdrawal + FUP Period: All patients who are treated with mirikizumab are considered to have entered this period.	Same as the “All Miri + Placebo Withdrawal Period.”	After the last study visit.

Abbreviations: FUP = follow-up; Miri = mirikizumab.

- ^a Missing dose time will be imputed as the earliest time that is consistent with available data about dose time. For example, suppose the minutes are missing but hour is present. In this case, we would impute the minutes to be 0.
- ^b The “All Miri Period” by definition excludes “the Placebo Withdrawal Period.” Thus, for patients who are re-randomized to placebo and then relapse, the “All Miri Period” is actually made up of two separate time periods with two separate start and end dates.

6.1.3. Definition of Study Baseline

For efficacy and health outcomes, study baseline is defined as the last non-missing assessment (including unscheduled visits) before the first injection, which in most cases will be the measure recorded at Week 0 (Visit 2). For efficacy/health outcome measures, if the patient does not take any injection, the last available value on or prior to the randomization date will be used. In cases where baseline measurements are taken on the same day as the injection, the baseline measurements are used as the baseline for data analysis.

For the Psoriasis Symptom Scale (PSS), the weekly average of at least 4 days of the consecutive 7 days prior to the first injection (or randomization, if the patient does not take any injection) will be the study baseline score.

Baseline for safety analysis is described in the Safety section (Section 6.13).

6.1.4. Analysis Methods

For assessments of the primary endpoints and other binary efficacy and health outcomes endpoints, the following will be provided:

- Crude proportions for each treatment group along with the 95% 2-sided asymptotic (i.e., not continuity corrected) confidence intervals (CIs) will be provided.
- The estimated common risk difference along with 95% CIs. The common risk difference (Agresti 2013) is the difference in proportions adjusted for the stratification factors as

mentioned in Section 6.2. SAS PROC FREQ will be used for the estimates and CIs, where the CIs are calculated by using Mantel-Haenszel-Sato method (Sato 1989).

- Cochran–Mantel–Haenszel (CMH) test will be used to compare the treatment groups while adjusting for the stratification factors as mentioned in Section 6.2. The CMH p-value will be reported, and the CMH adjusted odds ratio along with the 95% 2-sided asymptotic (i.e., not continuity corrected) CIs.

When specified as a sensitivity analysis for binary endpoints, logistic regression with a Firth penalized likelihood will be used. The model will include the treatment groups and the covariates described in Section 6.2. Firth correction is equivalent to specifying Jeffrey’s prior and seeking the mode of the posterior distribution. Roughly, it adds one-half of an observation to the data set, assuming that the true values of the regression parameters are equal to 0. The likelihood function is adjusted by a fixed quantity which reduces the positive bias of small samples. The fixed quantity is a function of the information which goes to 0 as sample size increases. Firth correction can be implemented in PROC Logistic by including “*firth*” as an option in the model statement. The odds ratio and the corresponding 95% CIs, as well as the treatment differences and the corresponding 95% CIs, will be reported.

In addition, when specified as a sensitivity analysis, pseudo-likelihood-based mixed-effects model of repeated measures (Categorical MMRM) estimating the percentage of patients achieving response across postbaseline visits may be used. When MMRM is used, the model includes treatment, baseline value (continuous), visit, the interaction of the baseline value-by-visit, the interaction of treatment-by-visit, and the induction/maintenance covariates mentioned in Section 6.2 as fixed factors. The binomial distribution and the logit link function will be used. The residual pseudo-likelihood with a subject-specific expansion (RSPL) will be used, which is equivalent to restricted maximum likelihood (REML). An unstructured covariance matrix will be used to model the within-patient variance-covariance errors. If the unstructured covariance matrix results in a lack of convergence, the heterogeneous Toeplitz covariance structure, followed by the heterogeneous autoregressive covariance structure will be used. The Kenward-Roger approximation will be used to estimate the denominator degrees of freedom. The Newton-Raphson with ridging optimization technique will be used to aid with convergence. The probability of response, the corresponding 2-sided 95% CI, and the p-value for the treatment comparisons at postbaseline visits will be reported.

Treatment comparisons of continuous efficacy and health outcome variables with multiple postbaseline measurements will be made using mixed-effects model for repeated measures (MMRM). When MMRM is used, the model includes treatment, baseline value, visit, the interaction of the baseline value-by-visit, the interaction of treatment-by-visit, and the induction/maintenance covariates mentioned in Section 6.2 as fixed factors. The covariance structure to model the within-patient errors will be unstructured. If the unstructured covariance matrix results in a lack of convergence, the heterogeneous Toeplitz covariance structure, followed by the heterogeneous autoregressive covariance structure will be used. The restricted maximum likelihood (REML) will be used. The Kenward-Roger method will be used to estimate the denominator degrees of freedom. Type III tests for the least squares (LS) means will be used for the statistical comparison; the 95% confidence interval will also be reported.

Treatment comparisons of continuous efficacy and health outcome variables with a single postbaseline time point will be made using analysis of covariance (ANCOVA) with the following in the model: treatment group, baseline value, and Induction Period/Maintenance Period covariates mentioned in Section 6.2. Type III tests for LSMeans will be used for statistical comparison between treatment groups. The LSMean difference, standard error, p-value, and 95% CI, unless otherwise specified, will also be reported. Analysis of covariance may also be used in addition to the MMRM approach, by repeating analysis for each time point.

The Kaplan-Meier (KM) product limit method will be used to estimate the survival for several time to event analyses. The hazard ratio and log-rank test stratified by covariates mentioned in Section 6.2 will be reported. Time for all analysis will be described in units of weeks.

For variables that are not collected at each postbaseline visit, data may exist at visits where the variable was not scheduled to be collected. In these situations, data from the early discontinuation visit that do not correspond to the planned collection schedule will be excluded from the MMRM analysis (Andersen and Millen 2013). For by-visit summaries/displays, such as boxplots, the weeks when data was not scheduled to be collected may not be displayed. However, unscheduled assessments within any defined study period will still be used in the shift analyses, and for imputing values for the change from baseline to modified baseline observation carried forward (mBOCF) endpoint analyses.

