5.2. Number of Participants

Approximately 650 participants will be screened to achieve 500 randomized participants: 400 randomized to mirikizumab and 100 randomized to placebo.

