	
(5) self-criticism;
	
Interest
	
Item #13 (general interest).
	
Domain is missing if the item is missing.

	
(6) suicidal ideation;
	
Energy/fatigue
	
Item #14 (energy level).
	
Domain is missing if the item is missing.

	
(7) interest;
	
Psychomotor agitation/retardation
	
The highest score recorded for the two psychomotor items: #15 (feeling slowed down) and #16 (feeling restless).
	
Domain is missing if all items are missing.

	
(8) energy/fatigue;
	
QIDS-SR16 Response
	
≥50% improvement in the QIDS-SR16 total score from baseline.
	
If total score is missing for baseline or visit, then missing.

	
(9) psychomotor agitation/retardation
	
QIDS-SR16 Remission
	
QIDS-SR16 Total Score of 0 to 5.
	
If total score is missing, then missing.

Measure	Description	Variable	Derivation/Comment	Definition of Missing Components
Facial Psoriasis	Physician assessed presence or absence of facial psoriasis.	Facial Psoriasis	Response is either Yes or No.	Missing if question is missing.

Abbreviations: BSA = body surface area; DLQI = Global Assessment Dermatology Life Quality Index; EMA = European Medicines Agency; HRQoL = health-related quality of life; MCID = Minimal Clinically Important Difference; MCS = Mental Component Score; NRS = Numeric Rating Scales; PASI = Psoriasis Area and Severity Index; PatGA = Patients Global Assessment of Psoriasis; PCS = Physical Component Score; Ps = psoriasis; PSS = Psoriasis Symptoms Scale; PSSI = Psoriasis Scalp Severity Index; SAP = statistical analysis plan; SDTM = study data tabulation model; sPGA = Static Physician Global Assessment; UK = United Kingdom; VAS = visual analog scale.

Table AMAK.6.6. Description of Efficacy/Health Outcomes Analyses

Measure	Variable	Analysis Method (Section 6.1.4)	Population (Section 6.1.1)	Time Point
PASI	PASI 90 (Primary and Sensitivity)	CMH analysis with NRI	Induction ITT; Induction PPS	Week 16 (and all visits in corresponding Periods)
		Logistic regression analysis with NRI	Induction ITT	Week 16 (and all visits in corresponding Periods)
		Categorical MMRM	Induction ITT	Week 16 (and all visits in corresponding Periods)
	PASI 75; PASI 90; PASI 100	CMH analysis with NRI	Induction ITT; Re-randomized Maintenance ITT;	All visits in corresponding periods
		Summary statistics with NRI and as observed	Non-re-randomized Maintenance; Re-randomized Relapsed	All visits in corresponding periods

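### SAP 6.1.4 names no formula for the per-arm 95% intervals of crude response rates; read as uncorrected Wald, they under-cover at the planned placebo rates (descriptive output only)

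*SAP*

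**What the plan says.** SAP section 6.1.4 applies to the primary endpoints and all other binary efficacy and health outcomes endpoints. Its first output is: "Crude proportions for each treatment group along with the 95% 2-sided asymptotic (i.e., not continuity corrected) confidence intervals (CIs) will be provided". No formula follows.

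The next item, the stratified common risk difference, does have a named method: "where the CIs are calculated by using Mantel-Haenszel-Sato method (Sato 1989"). The third item, the CMH adjusted odds ratio, reuses the asymptotic, no-continuity-correction description, so that description does not identify a formula for a single proportion.

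The planning rates are in SAP section 5.1:

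- Induction, PASI 90: "The assumed PASI 90 responses are 70% for the mirikizumab arm and 3% for the placebo arm".
- Induction, sPGA (0,1): "The assumed sPGA (0,1) responses are 70% for the mirikizumab arm and 5% for the placebo arm".
- Maintained PASI 90 at Week 52: "80% for 250 mg mirikizumab Q8W, 70% for 125 mg mirikizumab Q8W, and 10% for placebo", where "approximately 93 patients will be included in each treatment group".

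Protocol section 5.2 gives the induction sizes: "400 randomized to mirikizumab and 100 randomized to placebo". For PASI 90, SAP Table AMAK.6.6 sets the time point as "Week 16 (and all visits in corresponding Periods"); the sPGA (0,1) entry is equivalent.

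The visible text has no rule for zero or very low counts. Firth logistic regression and the categorical MMRM apply only where specified as sensitivity analyses, so they do not replace the crude-rate interval.

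**The concern.** An uncorrected Wald interval takes its width from the observed rate. When few responders are expected, a low count moves the interval down and narrows it at the same time, so it is most likely to miss when the count is low. The placebo arms here combine rates of 3%, 5% and 10% with about 100 or 93 patients, where this effect is noticeable.

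At stake is the honesty of a descriptive display. Placebo intervals labelled 95% would miss the true rate more often than one time in twenty, mostly by lying below it. Some could print as 0% to 0% or with a negative lower limit.

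**Working it through.** **Inputs, all from the plan.** Placebo: p=3% and p=5% with n=100; p=10% with n=93 (400 × 0.70 / 3 = 93.3). Active arms: 70% with n=400; 80% and 70% with n=93.

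**The plan's own figures.** The documents state no coverage figure beyond the nominal 95%. The power they state, above 95% for each planned comparison, reproduces: all four comparisons exceed 99.9% (100 vs 400 at two-sided 0.05; 93 per arm at two-sided 0.025). Power does not involve the per-arm interval.

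**Formulas**, with r = x/n and z = 1.96:

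- Wald: r ± z·√(r(1−r)/n).
- Wilson: centre (r + z²/2n)/(1 + z²/n); half-width [z/(1 + z²/n)]·√(r(1−r)/n + z²/4n²).
- Exact coverage: the sum of binomial probabilities P(X=x) over every x whose interval contains p.

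**Example, 3 of 100.** Wald: 0.03 ± 1.96·√(0.03·0.97/100) = 0.03 ± 0.033, or −0.3% to 6.3%. Wilson: 1.0% to 8.5%.

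**Which counts miss under Wald at the planned sizes.**

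- p=3%, n=100: x=0 gives 0% to 0%, and x=1 has upper limit 2.95%. Both lie below 3%: 0.0476 + 0.1471 = 19.5%. Counts of 9 or more lie above: 0.3%. Coverage is 80.2%.
- p=5%, n=100: x=0, 1 and 2 lie below 5% (the upper limit at x=2 is 4.74%): 0.0059 + 0.0312 + 0.0812 = 11.8%. Counts of 12 or more lie above: 0.4%. Coverage is 87.7%.
- p=10%, n=93: counts of 5 or fewer lie below (the upper limit at x=5 is 9.96%): 8.7%. Counts of 17 or more lie above: 1.0%. Coverage is 90.3%.

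So 98%, 97% and 89% of the misses are below the truth.

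**Nearby sample sizes.** Exact coverage oscillates with n, so it was also averaged over n=90 to 110 (3% and 5%) and n=84 to 102 (10%).

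| True placebo rate | Wald at planned n | Wald, nearby n: range (mean) | Wilson, nearby n: range (mean) | Clopper-Pearson mean |
|---|---|---|---|---|
| 3% | 80.2% | 79.8–94.7% (87.1%) | 94.1–97.8% (96.3%) | 98.5% |
| 5% | 87.7% | 85.2–94.5% (89.8%) | 92.7–97.0% (95.5%) | 97.5% |
| 10% | 90.3% | 90.3–95.0% (92.9%) | 93.3–96.4% (95.0%) | 96.6% |

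Wald is below 95% at every size in these windows; the 95.0% maximum at 10% is 94.99% before rounding.

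**Degenerate output at planned n** (rates 3%, 5%, 10%). Negative lower limit: 60.0%, 25.2% and 1.3% of trials. Interval of 0% to 0%: 4.8%, 0.6% and under 0.01%. Truncating the lower limit at 0 leaves coverage unchanged, because it cannot affect whether a positive true rate is inside.

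**Width.** Mean Wald against Wilson width is 6.3 vs 7.2, 8.3 vs 8.8 and 12.0 vs 12.2 percentage points.

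**Active arms, Wald vs Wilson.** 95.0% vs 94.4% (70%, n=400); 93.5% vs 94.9% (80%, n=93); 93.9% vs 94.6% (70%, n=93).

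**The case against.** The strongest reply is that the defect is conditional. The SAP's wording fits Wilson as well as Wald, and under Wilson there is no material under-coverage. The documents establish only that a formula is missing. This stands: every Wald figure above depends on taking the ordinary reading. The gap exists under either reading, however, and naming the method closes it.

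Second, no efficacy conclusion depends on these intervals. Protocol section 10.3.1 asks for an interval only on the treatment difference, so the per-arm interval is an SAP addition. With 3 of 100 on placebo, neither 6.3% nor 8.5% as an upper limit comes near an active rate of 70%. This also stands, and it is why the point is minor.

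Third, the shortfall is shown only at three assumed rates. The plan gives no placebo rates for PASI 75, PASI 100, BSA, PSS, DLQI or earlier visits, so nothing is quantified there. The maintenance case is mild, about two points on average. Both remarks are fair.

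Fourth, Wilson is not perfect: it dips to 92.7% at a true 5%, and in the 400-patient arm it covers slightly less than Wald. That is true, but small beside the Wald shortfall at the induction placebo rates.

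**Conclusion.** The concern holds as a minor point. SAP section 6.1.4 leaves the per-arm interval unnamed. On the ordinary Wald reading, and at the plan's assumed placebo rates, mean coverage near the planned sizes is about 87% (PASI 90), 90% (sPGA (0,1)) and 93% (maintained PASI 90), with lower values at exactly the planned sizes. The induction shortfall is clear and nearly one-sided; the maintenance shortfall is modest.

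The result rests on two assumptions: that Wald would be programmed, and that the true placebo rates are close to those in SAP section 5.1. The CMH analysis with NRI, the graphical multiplicity procedure, the Mantel-Haenszel-Sato interval and the sample size are unaffected.

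**What to change.** In SAP section 6.1.4, name the Wilson score interval for the crude per-arm proportions. Clopper-Pearson is an acceptable conservative alternative. Keep the Mantel-Haenszel-Sato interval for the risk difference. If a score interval was already intended, stating so is enough.

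One method can serve all arms, since Wilson covers 94.4% to 94.9% at the assumed active rates. The cost is one phrase in the SAP and the matching program option. The trade-off is occasional Wilson coverage near 93%, or somewhat wide placebo intervals with Clopper-Pearson.
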